7.4. Blinding

Participants will be randomly assigned to receive study treatment. Investigators will remain blinded to each participant's assigned study treatment throughout the course of the study. In order to maintain this blind, an otherwise uninvolved 3rd party (e.g., site pharmacist) will be responsible for the dispensation of all study treatment and will endeavor to ensure that there are no differences in time taken to dispense following randomization.

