9.3. Stopping Rules in Response to SAEs or Other Events

Dose-limiting toxicity AEs will be defined as Grade ≥ 3 , treatment-emergent, treatment-related laboratory abnormalities (Appendix 6) or AEs per the grading system by [US Department of Health and Human Services](#) (CTCAE, Version 5.0)The following Stopping Criteria will be used:

Clinical Findings:

1. Anaphylaxis or Grade ≥ 3 skin rash or pruritis
2. Grade ≥ 3 nausea, emesis or diarrhea

Laboratory Findings:

1. Evidence of new onset of acute renal or hepatic failure, defined by increases in BUN, creatinine, or LFTs (AST, ALT, Alkaline phosphatase) that reflect new evidence of Grade 3 thresholds for liver function tests, for creatinine, and for electrolytes attributable to the administration of drug in the context of the Investigator's evaluation.
2. Evidence of acute infection or inflammation, defined by changes in the WBC and differential, attributable to the administration of drug in the context of the Investigator's evaluation.
3. Any "unexpected" Grade ≥ 3 laboratory test result.

If one of the above clinical or laboratory criteria for stopping occurs in any subject, further study recruitment and subject dosing will be halted until a full safety assessment can be completed. Unblinding of the affected subject will be performed and the PI and Sponsor will review the totality of clinical data and any other circumstances possibly related to the "Stopping Criteria" findings to determine if the study can be resumed, modified, or will be permanently terminated.

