- When an AE/SAE occurs, it is the responsibility of the Investigator to review all documentation (e.g., hospital progress notes, laboratory reports, and diagnostics reports) related to the event.
- The Investigator will then record all relevant AE/SAE information in the CRF.
- It is **not** acceptable for the Investigator to send photocopies of the participant's medical records to ANA Therapeutics in lieu of completion of the AE/SAE CRF page.
- There may be instances when copies of medical records for certain cases are requested by ANA Therapeutics. In this case, all participant identifiers, with the exception of the participant number, will be redacted on the copies of the medical records before submission to ANA Therapeutics.

- The Investigator will attempt to establish a diagnosis of the event based on signs, symptoms, and/or other clinical information. Whenever possible, the diagnosis (not the individual signs/symptoms) will be documented as the AE/SAE.

Assessment of Intensity

The Investigator will make an assessment of intensity for each AE and SAE reported during the study and assign it to 1 of the following categories:

- Mild: An event that is easily tolerated by the participant, causing minimal discomfort and not interfering with everyday activities.
- Moderate: An event that causes sufficient discomfort and interferes with normal everyday activities.
- Severe: An event that prevents normal everyday activities. An AE that is assessed as severe should not be confused with a SAE. Severe is a category utilized for rating the intensity of an event; and both AEs and SAEs can be assessed as severe.

An event is defined as 'serious' when it meets at least 1 of the predefined outcomes as described in the definition of an SAE, NOT when it is rated as severe.

Assessment of Causality

- The Investigator is obligated to assess the relationship between study treatment and each occurrence of each AE/SAE.
- A "reasonable possibility" of a relationship conveys that there are facts, evidence, and/or arguments to suggest a causal relationship, rather than a relationship cannot be ruled out.
- The Investigator will use clinical judgment to determine the relationship.
- Alternative causes, such as underlying disease(s), concomitant therapy, and other risk factors, as well as the temporal relationship of the event to study treatment administration will be considered and investigated.

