- The Investigator will also consult the Investigator's Brochure (IB) and/or Product Information, for marketed products, in his/her assessment.
- For each AE/SAE, the Investigator **must** document in the medical notes that he/she has reviewed the AE/SAE and has provided an assessment of causality.

- There may be situations in which an SAE has occurred and the Investigator has minimal information to include in the initial report to ANA Therapeutics. However, **it is very important that the Investigator always make an assessment of causality for every event before the initial transmission of the SAE data to ANA Therapeutics.**
- The Investigator may change his/her opinion of causality in light of follow-up information and send a SAE follow-up report with the updated causality assessment.
- The causality assessment is one of the criteria used when determining regulatory reporting requirements.

Follow-up of AEs and SAEs

- The Investigator is obligated to perform or arrange for the conduct of supplemental measurements and/or evaluations as medically indicated or as requested by ANA Therapeutics to elucidate the nature and/or causality of the AE or SAE as fully as possible. This may include additional laboratory tests or investigations, histopathological examinations, or consultation with other health care professionals.
- If a participant dies during participation in the study or during a recognized follow-up period, the Investigator will provide ANA Therapeutics with a copy of any post-mortem findings including histopathology.
- New or updated information will be recorded in the originally completed CRF.
- The Investigator will submit any updated SAE data to the ANA Therapeutics within 24 hours of receipt of the information.

Reporting of SAEs

SAE Reporting to ANA Therapeutics via an Electronic Data Collection Tool

- The primary mechanism for reporting an SAE to ANA Therapeutics will be the electronic data collection tool.
- If the electronic system is unavailable for more than 24 hours, then the site will use the paper SAE data collection tool (see next section).
- The site will enter the SAE data into the electronic system as soon as it becomes available.

- After the study is completed at a given site, the electronic data collection tool will be taken off-line to prevent the entry of new data or changes to existing data.

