8.1. Adverse Events

Adverse Events will be coded according to the latest version of the MedDRA dictionary.

In each part of this study, surveillance of adverse events (AE) will begin from the day the subject signs the informed consent form (ICF) until the end of the study.

Adverse events shall be recorded starting at signing of ICF. AEs will be defined as treatment-emergent adverse events (TEAE), if they occurred after initiation of study treatment or if they started prior to study drug administration but worsened after dosing, given that worsening started within the treatment period. All AEs will be listed and flagged as treatment emergent or non-treatment emergent.

Only TEAEs shall be summarized by cohort/dose in the clinical study report. Other AEs will be included in the medical history and will be listed in subject listings.

An overall summary with number and percentage of subjects with all different TEAE categories, like treatment-related, serious, and leading to discontinuation (MAD part only) provided by cohort/dose. Incidence and severity of TEAEs will be summarized by cohort/dose within System Organ Class (SOC), and within Preferred Term (PT).

TEAEs will also be summarized by relationship per SOC and PT. Relationships will be categorized into related (includes “Related” and “Possibly Related”) and unrelated (includes “Not Related” and “Unlikely Related”).

Serious TEAEs and TEAEs leading to discontinuation (MAD part only) will be summarized by cohort/dose with the number and percentage of subjects with treatment-emergent adverse events classified SOC and PT.

All AEs will be listed by subject.

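### A stopping event opens the participant's code for a review that includes the PI, against the blinding section, and no rule fixes causality beforehand, so relatedness can be set knowing the arm

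*Protocol*

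**What the plan says.** Protocol 9.3 lists two clinical and three laboratory stopping criteria. One event in one participant is enough: "If one of the above clinical or laboratory criteria for stopping occurs in any subject", recruitment and dosing halt. The section then continues: "Unblinding of the affected subject will be performed and the PI and Sponsor will review the totality of clinical data". The unblinding is mandatory, and the text does not say who receives the code.

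Protocol 7.4 states: "Investigators will remain blinded to each participant's assigned study treatment throughout the course of the study". It gives no exception for stopping events or for emergencies.

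On causality, Protocol Appendix 4 says: "The Investigator is obligated to assess the relationship between study treatment and each occurrence of each AE/SAE". The investigator assigns intensity as well. Two further sentences in Appendix 4 govern timing and revision:

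- For SAEs, the investigator must "always make an assessment of causality for every event before the initial transmission of the SAE data to ANA Therapeutics". Later, "The Investigator may change his/her opinion of causality in light of follow-up information" and send an SAE follow-up report.
- For AEs and SAEs alike, "New or updated information will be recorded in the originally completed CRF".

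On use, SAP 8.1 says: "TEAEs will also be summarized by relationship per SOC and PT". It groups related with possibly related, and not related with unlikely related. SAP 1.3 has serious and drug-related adverse events inform MAD dosing, and uses aggregate summaries there to protect the blind. Protocol 9.3 makes relatedness part of the DLT definition.

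**The concern.** Both sections cannot be followed once a criterion is met. Section 7.4 keeps the investigator blind without qualification, while 9.3 opens the code and places the PI in the review that follows.

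The person who may then know the arm is also the person who decides whether the event is related. Nothing fixes that decision before the code is opened, marks a later change as made after unblinding, or says which value is analysed. Knowledge of placebo could pull a judgement towards unrelated, and knowledge of active drug towards related. Such a shift runs in opposite directions in the two arms. It would affect the few severe events that matter most in a small safety study.

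**Working it through.** **Step 1: what each trigger requires before the code is opened (Protocol 9.3).**

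| Criterion | Is attribution to drug part of the trigger? | Exposed to knowledge of the arm |
|---|---|---|
| Clinical 1 (anaphylaxis, severe skin reaction) | No | Initial call (if not an SAE) and any later change |
| Clinical 2 (severe GI event) | No | Initial call (if not an SAE) and any later change |
| Laboratory 1 (renal or hepatic) | Yes | Later change only |
| Laboratory 2 (infection or inflammation) | Yes | Later change only |
| Laboratory 3 (unexpected Grade 3 or higher) | No | Initial call (if not an SAE) and any later change |

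If the event is an SAE, Appendix 4 requires a causality call before initial transmission. That step is not ordered relative to opening the code, and it does not prevent a later change. For a non-serious event, Appendix 4 requires a documented causality assessment but sets no time for it.

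**Step 2: which outputs use relatedness.** SAP 2.2.1 defines the primary incidence measures as TEAEs, serious TEAEs and discontinuation due to a TEAE. None is counted by relatedness. Relatedness enters the SAP 8.1 summary, the SAP 1.3 input to MAD dosing, and the DLT definition in Protocol 9.3. The visible SAP plans no DLT table. Because SAP 8.1 collapses four categories into two, a move between unlikely related and possibly related is enough to change the table.

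**Step 3: weight of one reclassified event.** The plan states no figure on this point, so there is none to reproduce. The group sizes come from the cohort lists and agree with the enrolment totals: 3 × (8 + 2) = 30 and 3 × (9 + 3) = 36. The change in the related rate is 1/n:

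- SAD active, n = 8: 1/8 = 12.5 points.
- MAD active, n = 9: 1/9 = 11.1 points. The Protocol synopsis and SAP section 3 also give a 10:2 ratio, for which 1/10 = 10.0 points.
- SAD placebo: 1/2 = 50 points within one cohort. If pooled over three cohorts, 1/6 = 16.7 points; the SAP does not state that placebo will be pooled.

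**Step 4: spillover to the rest of the cohort.** In an 8:2 cohort, each other participant's probability of being on active drug starts at 8/10 = 80%. It becomes 7/9 = 77.8% if the opened code is active, or 8/9 = 88.9% if it is placebo. This is modest. The main exposure is the affected participant's own assessment.

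**Step 5: how often this could arise.** The documents give no per-participant risk of a stopping event. For assumed risks q of 1%, 2%, 5% and 10% over 30 + 36 = 66 participants, the chance of at least one is 1 − (1 − q)^66 = 49%, 74%, 97% and more than 99%.

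**The case against.** The strongest reply is that 9.3 is a specific safety rule and 7.4 a general one. Amendment 1 added 9.3 in response to FDA comments, and 7.4 was simply not updated; one cross-reference would cure the conflict. The SAP cites the protocol of 22 October 2020, so its silence on unblinded events may only reflect its age. The study is descriptive, and any single event weighs heavily among 8 people. Protocol 3.2.3 reports only mild or moderate side effects in 2385 evaluable patients, so severe events may be rare. That experience was at doses up to 2000 mg/day, whereas the SAD part goes to 3000 mg.

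Much of this stands. Unblinding for a safety review is not a fault, and the conflict between 7.4 and 9.3 is a matter of wording. The cross-reference does not, however, settle which causality assessment is tabulated.

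Several stronger readings are tempting, and the documents do not support them:

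- *The protocol hands the code to the PI.* That is the natural reading, since the PI reviews the data right after unblinding and nothing withholds the code, but it is not stated.
- *Causality may be revised freely for every event.* The revision sentence is worded for SAEs. For other events the only support is the general sentence on updating the CRF.
- *The halt can turn on an unblinded causality call.* Every criterion is judged before the code is opened, and laboratory criteria 1 and 2 already include attribution.
- *The primary endpoint is biased.* The primary incidence measures do not use relatedness, and the SAP plans no DLT count that could be distorted.
- *The PI should be denied the code.* That is a rule for handling safety events. The statistical point does not need it.

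**Conclusion.** The point holds in limited form. Protocol 7.4 and 9.3 conflict and must be reconciled. For non-serious events under the two clinical criteria or laboratory criterion 3, the initial causality call can be made with the arm known. For laboratory criteria 1 and 2, only later revision is exposed. SAEs need a call before transmission, but neither that call nor a later revision is tied to the time of unblinding.

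The outputs at risk are secondary to the primary incidence measures. Where one event is reclassified, the active-group rate moves by 10.0 to 12.5 points, depending on the part and on which MAD ratio applies. The conclusion assumes that the PI learns the arm during the review and is among those who assign causality. It shows that bias is possible, not that it will occur. The frequency range rests on assumed risks.

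**What to change.** 1. In Protocol 7.4, name 9.3 as an exception to the blind, and state in 9.3 who receives the code.
2. In 9.3, have the investigator record and date grade and causality before reading the code, without delaying the halt, participant care or any urgent unblinding.
3. In SAP 8.1, tabulate relatedness from that dated entry. List later changes separately, flagged as made after unblinding. Any DLT classification and the drug-related events considered under SAP 1.3 should use the same entry.
4. Make these edits when the SAP is brought up to Amendment 1.

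The cost is one short CRF entry per stopping event and one extra listing. When to halt or unblind is left as a clinical matter, and no change to it is proposed.

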9.4. Treatment of Overdose

For this study, any dose of ANA001 greater than 3000 mg within a 24-hour time period will be considered an overdose.

In the event of an overdose, the Investigator should:

1. Contact the Medical Monitor immediately.
2. Closely monitor the participant for any AE/SAE and laboratory abnormalities until ANA001 can no longer be detected systemically (at least 7 days).
3. Document the quantity of the excess dose as well as the duration of the overdose in the CRF.

Decisions regarding dose interruptions or modifications will be made by the Investigator in consultation with the Medical Monitor based on the clinical evaluation of the participant.

9.5. Pharmacokinetics

Whole blood samples of approximately 4 mL will be collected for measurement of plasma concentrations of ANA001 as specified in the SoA (Section 2). Additional samples may be collected during the study if warranted and agreed upon between the Investigator and the Sponsor.

Instructions for the collection and handling of biological samples will be provided by the Sponsor. The actual date and time (24-hour clock time) of each sample will be recorded.

Any changes in the timing or addition of time points for any planned study assessments must be documented and approved by the relevant study team member and then archived in the Sponsor and site study files, but will not constitute a protocol amendment. The IRB/IEC will be informed of any safety issues that require alteration of the safety monitoring scheme or amendment of the ICF.

The following PK parameters for ANA001 will be estimated using actual sample collection times:

C_{\max}	maximum plasma concentration during a dosing interval
C_{\min}	minimum plasma concentration during a dosing interval
t_{\max}	time to reach the maximum plasma concentration
AUC_t	area under the plasma concentration-time curve from time 0 to time t after dosing
$AUC_{0-\text{last}}$	area under the plasma concentration-time curve from time 0 to time the last quantifiable concentration
$AUC_{0-\infty}$	area under the plasma concentration-time curve from time 0 to infinity
$t_{1/2}$	elimination half-life associated with the terminal slope (λ_z) of the semilogarithmic drug concentration-time curve, calculated as $0.693/\lambda_z$
CL/F	Systemic clearance
V_z/F	Volume of distribution

9.6. Medical Resource Utilization and Health Economics

Not applicable.

10. Statistical Considerations

10.1. Sample Size Determination

Sample size was not based on statistical considerations.

10.2. Populations for Analyses

For purposes of analysis, the following populations are defined:

Population	Description
Enrolled	All participants who sign the ICF
Safety	All participants randomly assigned to study treatment and who take at least 1 dose of study treatment. Participants will be analyzed according to the treatment they actually received.
Pharmacokinetic	All participants randomly assigned to study treatment, who take at least 1 dose of study treatment, and contribute at least 1 post-dose evaluable PK sample. Participants will be analyzed according to the dose they actually received.

10.3. Statistical Analyses

The statistical analysis plan will be developed and finalized before database lock and will describe the participant populations to be included in the analyses, and procedures for accounting for missing, unused, and spurious data. This section is a summary of the planned statistical analyses of the primary and secondary endpoints.

10.3.1. Safety Analyses

All safety analyses will be performed on the Safety Population. Safety parameters will include frequency of treatment-emergent AEs (TEAEs), SAEs, study drug discontinuation due to an AE (MAD portion only), concomitant medication use, and changes from baseline in clinical laboratory results, vital signs, ECG, and physical examinations. TEAEs are defined as AEs that started or worsened after dosing. Adverse events will be coded using the latest version of the Medical Dictionary for Regulatory Activities. A list of participants who have SAEs and who discontinue from the study due to an AE will be provided. Treatment-emergent AEs will be summarized by system organ class and preferred term for each dose level.

Individual results of laboratory tests (chemistry, hematology, and urinalysis) will be listed and summarized. Baseline, post-dose, and change from baseline to post-dose laboratory data will be summarized by dose. Individual results of vital signs will be listed and summarized. Observed values and changes from baseline in vital signs will be summarized by dose. Individual results of ECG parameters from the 12-lead safety ECGs will be listed and changes from baseline will be

summarized by dose. Physical examination findings and concomitant medication use will be presented in data listings.

10.3.2. Pharmacokinetic Analyses

The non-compartmental PK analyses will be described in the Statistical Analysis Plan finalized before database lock. Plasma concentrations of ANA001 will be summarized by dose over each scheduled sampling time using descriptive statistics. Individual plasma concentration data versus actual time points will be presented in listings. Pharmacokinetic parameters of ANA001 will be summarized by dose using descriptive statistics. Individual PK parameters will be presented in a data listing. Dose proportionality will be assessed graphically and using the power model.

Appendix 1: Abbreviations and Terms

ANA	ANA Therapeutics, Incorporated
API	Active pharmaceutical ingredient
ARDS	Acute respiratory distress syndrome
AUC	Area under curve
BID	Twice daily
BSL	Bio-safety Level
CL	Clearance
Cmax	Maximum serum concentration
CoV	Coronavirus
COVID-19	Coronavirus disease of 2019
CYP	Cytochrome P450
DG	Dose group
DLT	Dose-limiting toxicity
DMC	Data monitoring committee
DMSO	Dimethylsulfoxide
DP	Drug product
DS	Drug substance
EC50	Half-maximal effective concentration
ECMO	Extracorporeal membrane oxygenation
IC50	Half-maximal inhibitory concentration
FDA	Food and Drug Administration
GI	Gastrointestinal
GLP	Good laboratory practice

HDPE	high-density polyethylene
HTD	Human therapeutic dose
ICH	International Council for Harmonization of Technical Requirements for Pharmaceuticals for Human Use
IL	Interleukin
LD50	Half-maximal lethal dose
LLN	Lower limit of normal
MERS	Middle East respiratory syndrome
MRT	Mean residence time
NA	Not applicable
NDA	New drug application
NF- κ B	Nuclear factor kappa-light-chain-enhancer of activated B cells
PBS	Phosphate buffered saline
PK	Pharmacokinetic
PO	By mouth
PVA	Polyvinyl alcohol
SAE	Serious adverse event
SARS	Severe acute respiratory syndrome
SBA	Summary basis for approval
STAT	Signal transducers and activators of transcription
SUSAR	Suspected unexpected serious adverse reaction
t _{1/2}	Elimination half-life
TID	Thrice daily
t _{max}	Time take to reach C _{max}

TMEM16A	Transmembrane member 16A
TNF- α	Tumor necrosis factor-alpha
ULN	Upper limit of normal
VSS	Volume of distribution at steady state
WBC	White blood cell
WHO	World Health Organization

